**4.3 REGISTRY.** Registry data will be used to determine the outcome of the non-randomized (treated), and untreated SVA study population to examine the impact and outcome of alternative treatment approaches. This includes fetal *AF with hydrops*, which is not studied by a separate RCT due to the rarity of the association.

**4.4 STUDY WITHDRAWAL.** A subject is free to withdraw from participation in the trial at any time, for any reason, specified or unspecified, and without prejudice. The reason for the subject's withdrawal from the study (if given) will be documented in the *Study Completion/Exit Form*. If the subject withdraws, data that has already been collected up to that point in time will be kept (as indicated in the patient informed consent).

**4.5 PARTICIPANT REPLACEMENT.** Study participants withdrawing from the trial will be replaced 1:1 to obtain the target number of evaluable participants per RCT arm.

**4.6 NONPARTICIPATION.** If an eligible patient has been approached for the RCT but elects to not participate the screening information should still be documented in REDCap, including the patient's decision to not participate. Collection of basic screening information by the sponsor is important as it will allow an analysis of patient willingness to participate, of excluded cases and an estimation of the number of total SVA cases. Moreover, information on the rate of non-participation will be essential for future publications.

## 5. STUDY SAFETY

**5.1 SAFETY PROCEDURES.** The FAST RCTs will assess *standard prenatal treatment* that has been used for decades because the fetus suffers from a life-threatening yet treatable cardiac condition and other management options including direct treatment or premature delivery are considered more invasive, more harmful, or both. Perinatal demise is not an unusual outcome of hydropic fetuses with SVA, irrespective of the choice of treatment. Health Canada, FDA (US) and MHRA (UK) have approved all three RCT sub-studies. There is extensive data on the safe use of the study agents for this indication. Minor drug-related maternal AEs are not infrequent [monographs], but maternal SAEs owing to fetal antiarrhythmic drug therapy have not been reported. However, virtually all antiarrhythmics have proarrhythmic potentials to provoke new or exacerbate existing

arrhythmias. This risk increases with toxic drug levels, maternal heart disease, preexisting ventricular arrhythmia, and hypokalemia.

Procedures for study participants to minimize the risk of SAEs include:

- only mothers without serious health and pregnancy concerns other than fetal SVA are eligible for participation in RCT sub-studies (**see 7**);
- the primary physician and participant both are informed about the assigned drug therapy from the time of randomization to study end (open label trial);
- drug dosages will be used that are considered to be safe and effective, thus avoiding toxic levels (digoxin) and excessive QTc prolongation >0.5 (sotalol); d) concomitant medication (7.6.2) that may interact with a study drug are not to be used or, if no alternative exists, used with caution during the trial; and
- initiation of therapy is recommended in-hospital to monitor maternal/fetal heart rates and wellbeing, followed by serial outpatient encounter once arrhythmia control is achieved.

**5.2 ADVERSE EVENT ASSESSMENT AND DOCUMENTATION.** A main objective of FAST RCTs is patient safety. This is accomplished by the systematic recording of AEs.

**Adverse Event (AE):** is defined as **any untoward medical occurrence of a symptom that may or may not have a causal relationship with the treatment used.** Examples include a rash noted during a physical exam, abnormal lab results, or a change from a baseline condition.

Failure of the drug does not constitute an AE. Sources of information will include observation (physical exam; ECG; echo; lab result), patient statement, patient charts, and serial assessment at each encounter by questionnaire for changes from baseline (↑ severity/frequency of pre-existing symptom(s)) or new AEs).

It will be the responsibility of the primary physician to identify, and to classify the seriousness, severity, causality and expectedness of an AE as follows:

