**b) Severity assessment:**

Mild	Events are considered MILD if signs/symptoms are mild, clinical relevance is marginal, laboratory findings are asymptomatic and no specific medical intervention is required.
Moderate	Events are considered MODERATE if they require minimal, local, or non-invasive intervention only.
Severe	Events are considered SEVERE if they interrupt the participant's normal daily activities and generally require systemic drug therapy or other treatment; they are usually incapacitating.

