## 7. CONDUCT OF THE RCTs

The Table of Events below summarizes the different study steps from the time of prenatal identification and randomization to study end as they relate to the RCT sub-studies.

Procedures and Tests	Pre-treatment	Fetal Treatment		Postnatal Birth to 30(+) days
		Day 1	Day 2 - Birth	
Fetal echo: Diagnosis -SVA (M-mode; Doppler) - Fetal state	X diagnosis and data ⬆ Images within 1 week recommended		X data each visit ⬆ if changed	
Maternal 12-lead ECG	X required prior to treatment start ⬆		X recommended within 1 week of treatment start and repeated at every significant change in treatment/increase in dose ⬆ if changed	
Maternal exams: - BP, HR	X		X recommended within 1 week of treatment start and during maintenance therapy	
Maternal tests: - K, Ca - serum creatinine	X			
Maternal and pregnancy history	X			
Maternal consent	X			
Eligibility Assessment - PI	X			
Randomization	By sites in REDCap			
Hospitalization		Recommended	If indicated	If indicated
Treatment initiation		X		
Review of current treatment - Drugs, dosages, intervals			X each visit	X
Review of clinical findings			X each visit	X
Review of test results - Digoxin level (if relevant)			X each visit	
- Home fetal heart rate monitor (FHRM)			⬆ or enter data	
Adverse event assessment			X each visit	X
Compliance assessment (1st line therapy)			X each visit	
Review of prenatal outcome			X at birth/IUD	
Neonatal 12-lead ECG in sinus rhythm				X ⬆
Neonatal 12-lead ECG tracing in SVA				X ⬆ if present
Review of neonatal outcome				X at 30(+)days/NND
Review of maternal outcome				X

X = data entry into REDCap, ⬆= uploaded in REDCap

Patient identification, data entry, eligibility screening, randomization (Pre-treatment) and treatment initiation (Day 1) are to occur on the same day if there is an immediate need of fetal treatment.

**7.1 PATIENT IDENTIFICATION.** The site investigator will be responsible for identifying and recruiting RCT participants and conducting the study at the participating center. The investigator will inform a patient who fulfills eligibility criteria about the study early on with the help of a *Patient Brochure*.

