### **AF WITHOUT HYDROPS (RCT A): DIGOXIN vs. SOTALOL**

#### **RCT A ARM 1: DIGOXIN**

Aim: therapeutic maternal trough level of 1.0-2.0 ng/ml or 1.3-2.6 nmol/L (please verify the units your laboratory reports).

→ *Oral or intravenous* loading dose: **Initiate treatment with 0.5 mg Digoxin q 12 h** (total 4 doses over 48 hours) followed by:

→ *Oral maintenance dose:* it is recommended to obtain maternal digoxin trough level 12 hours after the 4th loading dose just prior to the administration of the 1st maintenance dose\* → await the result and adjust the 1st maintenance dose according to the trough digoxin level as followed:

(\*alternatively, a digoxin level may be obtained prior to the 4th dose to adjust the 1st maintenance dose if levels are not rapidly measured in your center)

Trough level (nmol/L)	Trough level (ng/ml)	Maintenance digoxin dose	Route
2.6 to <2.9	2 to <2.3	0.25 mg/day	Oral
1.9 to <2.6	1.5 to <2	0.375 mg/day	Oral
1.5 to <1.9	1.2 to <1.5	0.5 mg/day	Oral
1.0 to <1.5	0.8 to <1.2	0.75 mg/day	Oral
<1.0	<0.8	1 mg/day	Oral
≥2.9	≥2.3	0 mg/day until digoxin level is <2 ng/ml	

→ recommended to repeat maternal trough level until steady state therapeutic drug levels are obtained. *If using IV Digoxin loading see additional recommendations for IV Digoxin administration below.*

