**RCT B ARM 2: FLECAINIDE**

Aim (if available): therapeutic maternal drug level of *0.2-1 µg/ml*

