#### **SECONDARY OUTCOME**

- Proportion of participants with cardioversion over time
- Proportion of participants with treatment failure
  - Number of participants with treatment failure compared to number of participants with successful treatment.
  - Treatment failure is defined as one of the following:
    1. cross-over to another drug
    2. SVT/AF that persists to birth
    3. preterm birth
    4. death
- Cause of death (prenatal, postnatal)
- Proportion of participants with arrhythmia related death
- Average gestational age at birth
- Birth weight (z-scores)
- Average days of maternal and neonatal hospitalization related to SVA therapy
- Maternal prevalence of pregnancy/treatment-related AEs and outcomes
- Proportion of AEs / adverse outcomes (prenatal, postnatal)

The primary outcome measure is absolute (term delivery without tachyarrhythmia) with no room for interpretation. Secondary outcomes will be the time interval from treatment initiation to the beginning of permanent cardioversion, and once established, the freedom from SVA recurrence on maintenance therapy. Only the final outcome will be considered to classify cases. Cross-over to another agent, fetal demise, development of fetal hydrops, and delivery for SVA will be considered treatment failures. Any recurrence of fetal SVA after

documentation of a normal cardiac rhythm >24 hours by echocardiography will be classified as maintenance treatment failure.

**7.11 STATISTICAL ANALYSES.** All statistical analyses using SAS (SAS Institute, Cary NC) with standard settings will be performed by very experienced statistician from the Cardiovascular Data Management Centre (CVDMC) at SickKids. As a general precept, all 3 RCTs will be analyzed separately. RCT analyses will be performed on an *intention-to-treat basis*, although a separate subgroup analysis will be performed. Descriptive statistics for all study variables, for each study groups separately, will be created using means with standard deviation, median with inter-quartile range, and frequencies as appropriate. Baseline characteristics that should be equally distributed between groups through randomization (age at diagnosis, baseline fetal heart rate, incessant vs. intermittent SVA, maternal age) will be assessed in a test of randomization. The test of randomization will be performed using Fisher’s exact test for categorical variables and Student’s t-test (with Satterthwaite method for variance estimation) for continuous variables.

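### In RCT A and B the comparator arm has far less scheduled opportunity than the digoxin arm to record a laboratory adverse event, and AE proportions are secondary outcomes

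*Combined protocol and SAP*

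**What the plan says.** Section 5.2 defines an AE as "any untoward medical occurrence of a symptom that may or may not have a causal relationship with the treatment used" and then gives instances: "Examples include a rash noted during a physical exam, abnormal lab results, or a change from a baseline condition". It adds: "Sources of information will include observation (physical exam; ECG; echo; lab result), patient statement, patient charts". The severity table in 5.2 b) grades an event as mild when, among other things, "laboratory findings are asymptomatic and no specific medical intervention is required".

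In the Table of Events (section 7), potassium, calcium and creatinine appear only in the pre-treatment column. The one blood test listed during fetal treatment is "Digoxin level (if relevant", at each visit. The prenatal encounter list in section 7.8 likewise names the digoxin level and no other blood test. It captures the maternal ECG whatever the arm.

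In section 7.6, the text for the digoxin arm of RCT A, repeated for RCT B, reads "recommended to repeat maternal trough level until steady state therapeutic drug levels are obtained". The sotalol arm of RCT A names no blood test. The flecainide arm of RCT B has "Aim (if available): therapeutic maternal drug level of" 0.2-1 µg/ml, a level that appears neither in the Table of Events nor in the section 7.8 list.

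Section 7.10 lists maternal AE prevalence and "Proportion of AEs / adverse outcomes (prenatal, postnatal" among the secondary outcomes. Section 7.11 compares binary secondary outcomes between arms in the same way as the primary outcome, and the interim safety report reviews between-group differences.

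**The concern.** A between-arm AE comparison is fair only if both arms are searched for AEs with similar intensity. Symptoms, examination, ECG and echo are sought in both arms. Laboratory findings are not: in RCT A and B the scheduled on-treatment test follows the drug, and the drug is the randomised factor.

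The plan foresees digoxin results outside its aim of 1.0-2.0 ng/ml, since the dose tables in 7.6 have rows for 2 to <2.3, for ≥2.3 and for <0.8 ng/ml. Section 5.2 does make exclusions (drug failure, symptoms no worse than baseline, and the common pregnancy, birth and neonatal events of 5.2.1), but none covers an off-target drug level. The trial is open label and the treating physician classifies AEs, so sites may also differ in how they handle such a result.

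At stake is the direction of a safety conclusion. Digoxin could look less safe than sotalol or flecainide partly because its blood level is measured.

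**Working it through.** **Text check: is ascertainment unequal?**

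| | RCT A digoxin | RCT A sotalol | RCT B digoxin | RCT B flecainide |
|---|---|---|---|---|
| K, Ca, creatinine on treatment (section 7) | not scheduled | not scheduled | not scheduled | not scheduled |
| Drug level in arm description (7.6) | repeat troughs recommended | none named | repeat troughs recommended | aim, if available |
| Drug level in Table of Events and 7.8 list | yes | only if digoxin is given later | yes | only if digoxin is given later |
| Symptoms and ECG | yes | yes | yes | yes |

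In RCT C both arms receive digoxin under the same level instructions, so the asymmetry does not arise.

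**Inputs for an illustration.** The plan gives no figure on this point. Arm sizes come from section 3.2, and they reproduce with the usual formula (two-sided 0.05, 80% power):

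- RCT A: [1.96·√(2·0.40·0.60) + 0.842·√(0.30·0.70 + 0.50·0.50)]² / 0.20² = 93 per arm.
- RCT B: [1.96·√(2·0.65·0.35) + 0.842·√(0.55·0.45 + 0.75·0.25)]² / 0.20² = 88.1, rounded up to 89 per arm.

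Everything else is assumed: a true risk b of any AE, equal in both arms; a share s of digoxin mothers with a level recorded as an AE, independent of other AEs; none in the comparator arm; and mothers as the unit of analysis.

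**Formulas.** Recorded risk on digoxin: p_D = b + (1 − b)·s. With d = p_D − b and p̄ the mean of the two risks, the chance of a significant excess on digoxin is

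Φ{ [d√n − 1.96·√(2p̄(1 − p̄))] / √(b(1 − b) + p_D(1 − p_D)) }.

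Without any artefact it is 2.5% in that direction.

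**Example.** For n = 93, b = 0.40, s = 0.10: p_D = 0.40 + 0.60·0.10 = 0.46 and p̄ = 0.43. The expression is (0.579 − 1.372)/0.699 = −1.136 before rounding, and Φ = 0.128.

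| b | s | Recorded AE risk, digoxin vs comparator | Difference | n = 93 (RCT A) | n = 89 (RCT B) |
|---|---|---|---|---|---|
| 20% | 10% | 28% vs 20% | 8 points | 24.6% | 23.8% |
| 20% | 20% | 36% vs 20% | 16 points | 68.4% | 66.4% |
| 40% | 10% | 46% vs 40% | 6 points | 12.8% | 12.4% |
| 40% | 20% | 52% vs 40% | 12 points | 37.4% | 36.1% |
| 60% | 10% | 64% vs 60% | 4 points | 8.1% | 7.9% |
| 60% | 20% | 68% vs 60% | 8 points | 20.4% | 19.7% |

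With s from 5% to 30% and b from 20% to 60%, the difference runs from 2 points (0.40·0.05) to 24 points (0.80·0.30).

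**Second set of assumptions.** Suppose that half of the affected mothers have no other AE. At b = 40%, shares of 10% and 20% then add 5 and 10 points. Exact enumeration of two binomials with the two-sided Wald test gives 10.0% and 26.9% at 93 per arm, and 10.2% and 25.7% at 89 per arm. With no artefact it gives 4.7% and 5.1%. At b = 80% with s = 10% under independence, the shift is 0.20·0.10 = 2 points and the chance is about 6%.

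**The case against.** A reader might infer that the digoxin arm collects AEs which the comparator arm cannot have, and that the digoxin level is the only on-treatment blood test in the plan. The documents support neither. AE sources in every arm include laboratory results and patient charts. RCT B names an optional flecainide level. Under section 7.7 the physician may add or switch drugs at any time, so a comparator mother may later receive digoxin and have levels taken, and under intention-to-treat her AEs count in the comparator arm. The opportunity is unequal; it is not confined to one arm.

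A reader might also infer that every off-target level enters the AE record. That is not stated. The definition speaks of a symptom. The recording rule in 5.2 d) concerns new or worsened signs and symptoms. Section 7.6 uses levels to adjust the maintenance dose, and section 7.8 lists the digoxin level apart from adverse symptoms. The severity table grades an event once it is an AE and does not define one. Repeat troughs are recommended, not required.

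Finally, symptom-free levels are not meaningless for safety: sections 2.6 and 5.1 link toxic drug levels to proarrhythmic risk. Dropping them altogether from the AE comparison would be debatable.

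All of this stands and limits the point. It does not remove it. The definition's own examples include laboratory results, the mild grade covers asymptomatic ones, no exclusion mentions drug levels, and scheduled testing still differs by arm, most clearly in RCT A.

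**Conclusion.** The point holds as one of unequal opportunity. In RCT A and B, laboratory AEs are scheduled to be found mainly where digoxin is given, and the plan does not say whether an off-target level without symptoms counts. If sites record such levels, the secondary AE comparison is biased against digoxin. If none does, the effect is zero.

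The size cannot be derived from the documents. Under the stated assumptions it depends heavily on the underlying AE rate: it is substantial when few mothers otherwise have an AE and nearly vanishes when most do. The illustration also needs a per-mother denominator, which section 7.10 does not state, and it leaves out comparator levels, which would narrow the gap.

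The primary outcome and RCT C are untouched. The change should be made because it concerns a safety comparison and costs little, but it does not threaten the trial's main conclusion.

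**What to change.** In section 5.2, reconcile the word *symptom* in the AE definition with the asymptomatic laboratory findings that the severity table admits. State that a drug-level result with no new symptom, sign or ECG change is recorded and flagged *level only* in every arm, including any flecainide level and any digoxin level after add-on or switch, and that it stays visible to the DSMB. Reconcile the flecainide level in 7.6 with the Table of Events and the 7.8 list, so that results that are obtained are captured.

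In section 7.11, tabulate level-only findings separately by arm. Base the main between-arm AE comparison in RCT A and B on events ascertained the same way in both arms, with the total including level-only findings shown alongside. High levels then remain in view and the reader can see how much of any difference they account for.

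The cost is one extra flag on the AE worksheet, one extra table and a few sentences. The downside is that the main AE figure no longer includes level-only findings.

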***a) Assessment if event qualifies as serious:***

**Serious Adverse Event (SAE):** A SAE is any untoward medical occurrence that at any dose:

- Results in death,
- Is life-threatening,
- Requires inpatient hospitalization or prolongation of existing hospitalization,
- Results in persistent or significant disability/incapacity
- Results in congenital abnormalities or birth defect

Other events may be treated as SAEs if the Principal Investigator considers it to be an important medical event that may jeopardize the participant or require intervention to prevent one of the other outcomes listed above.

**b) Severity assessment:**

Mild	Events are considered MILD if signs/symptoms are mild, clinical relevance is marginal, laboratory findings are asymptomatic and no specific medical intervention is required.
Moderate	Events are considered MODERATE if they require minimal, local, or non-invasive intervention only.
Severe	Events are considered SEVERE if they interrupt the participant's normal daily activities and generally require systemic drug therapy or other treatment; they are usually incapacitating.

**c) Causality assessment:**

Definitely related	There is a certainty that the event is related to the study drug(s).
Probably related	There is high likelihood that the event is related to the study drug(s).
Possibly related	There is a likelihood that the study drug(s) is the cause of the event, but other causes cannot be ruled out.
Unlikely related	It is not likely that the event is related to the study drug(s), and other more likely causes are present.
Unrelated	Evidence exists that the event is related to something other than a study drug.

**d) Expectedness assessment:**

An event is considered unexpected if the nature, severity or frequency **is not consistent with the risk information listed in the *Product Monograph***.

Pregnancy- and treatment-related AEs will be documented by the site investigator. Prior to the start of drug therapy (pretreatment forms), a thorough medical history should be obtained to document all preexisting maternal symptoms, complaints and health concerns. As many pregnancy related symptoms are intermittent in nature, a thorough history including variations in severity and frequency should be taken. AEs should be reassessed at each participant encounter. If signs or symptoms remain similar to baseline or are less in severity, frequency, or both, they will be considered within the usual range and do not need to be documented as AEs. In contrast, signs and symptoms that are new or, if preexisting, are more frequent/severe, need to be documented, assessed for severity and causality, and followed up until resolution.

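### Two consecutive sentences in Section 5.2 d) overlap: a pre-existing symptom that is milder but more frequent than at baseline, or rarer but worse, is both exempt from AE documentation and required to be documented

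*Combined protocol and SAP*

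**What the plan says.** The rule for pre-existing symptoms is in Section 5.2, at the end of part d) Expectedness assessment. A baseline history is taken before treatment, including how complaints vary in severity and frequency, and AEs are reassessed at each encounter. Two sentences then decide what is recorded.

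- Exemption: "If signs or symptoms remain similar to baseline or are less in severity, frequency, or both, they will be considered within the usual range". The sentence goes on to say that such symptoms need no AE record.
- Documentation duty: "signs and symptoms that are new or, if preexisting, are more frequent/severe, need to be documented, assessed for severity and causality", and then followed to resolution.

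Two other statements in Section 5.2 bear on the question. The AE definition is illustrated as follows: "Examples include a rash noted during a physical exam, abnormal lab results, or a change from a baseline condition". The list of information sources has the questionnaire look, at each encounter, for an increase in "severity/frequency of pre-existing symptom(s)) or new AEs".

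On responsibility, Section 5.2 states: "It will be the responsibility of the primary physician to identify, and to classify the seriousness, severity, causality and expectedness of an AE". Part d) has the site investigator document the events. Section 5.1 makes the trial open label: physician and participant both know the assigned drug. Section 7.10 lists the maternal prevalence of pregnancy- or treatment-related AEs among the secondary outcomes.

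**The concern.** In the exemption, the words after the comma make a reduction in either dimension sufficient. In the documentation duty, the slash is most naturally read as an increase in either dimension being sufficient. Two either-dimension rules pointing in opposite directions must collide when the dimensions move apart. An invented example is a mother with occasional severe nausea before treatment who has mild nausea every day on treatment. The first sentence exempts her symptom and the second requires it to be documented.

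Such cases are foreseeable. Part d) itself notes that pregnancy symptoms often come and go, and asks for both dimensions at baseline. Nausea, headache and dizziness are listed in Section 2.4 as effects of both digoxin and flecainide. They are absent from the list of common pregnancy events in Section 5.2.1, which has its own recording rule, so the rule in part d) governs them.

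At stake is the consistency of the maternal AE count. Section 5.2 presents patient safety as a main objective, met by recording AEs systematically, and a rule that can be applied in two ways does not deliver that. About 50 centres are planned (Section 3.2), so different readings at different sites are a realistic possibility.

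**Working it through.** The plan gives no figure to reproduce. The check is one of logic: take every combination of change from baseline and ask which sentence it falls under.

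Inputs, all from Section 5.2:

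- Severity may be less, the same or more than at baseline, and so may frequency: 3 × 3 = 9 combinations.
- Exemption, read literally: both the same, or severity less, or frequency less.
- Documentation duty, slash read as or: severity more, or frequency more.
- Documentation duty, slash read as and: severity more and frequency more.

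| Severity | Frequency | Exempt (literal) | Document (slash = or) | Document (slash = and) |
|---|---|---|---|---|
| less | less | yes | no | no |
| less | same | yes | no | no |
| less | more | **yes** | **yes** | no |
| same | less | yes | no | no |
| same | same | yes | no | no |
| same | more | no | yes | no |
| more | less | **yes** | **yes** | no |
| more | same | no | yes | no |
| more | more | no | yes | yes |

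*Literal exemption, slash = or.* 6 combinations are exempt and 5 must be documented. 6 + 5 = 11, which is 2 more than 9. The 2 counted twice are the opposite-direction changes. None is uncovered.

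*Literal exemption, slash = and.* 6 are exempt and 1 must be documented: 6 + 1 = 7. The overlap has gone, but 9 − 7 = 2 combinations (one dimension worse, the other unchanged) now fall under neither sentence.

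So the literal exemption leaves an overlap or a gap whichever way the slash is read.

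The same count can be made with a narrower exemption, under which neither dimension may be worse. This exempts 4 combinations.

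*Narrow exemption, slash = or.* 4 + 5 = 9, with no overlap and no gap.

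*Narrow exemption, slash = and.* 4 + 1 = 5, leaving 9 − 5 = 4 uncovered.

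Only the narrow exemption combined with the slash read as or places all 9 combinations under exactly one rule.

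The other two statements do not supply the missing tie-break. The source list in Section 5.2 speaks of an increase but uses the same undefined slash. The AE example speaks of a change from baseline without giving a direction. Both lean towards recording, and neither addresses dimensions that move apart.

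**The case against.** The strongest reply is that the sentences can be reconciled. The exemption is permissive, since it says only that documentation is not needed, whereas the following sentence imposes a duty. A site that records a mixed change complies with both; a site that omits it breaches the second. The second sentence also opens with a phrase of contrast, so the two were evidently meant to be mutually exclusive, and the other statements in Section 5.2 lean towards recording. This argument stands as evidence of intent, and it makes the defect a drafting slip. It does not remove the problem, because a coordinator who reads the exemption as written can leave out a worsened symptom and point to a sentence that allows it.

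It is also fair to say that much of the information is collected anyway. Section 7.8 has maternal adverse symptoms captured by questionnaire at encounters and entered in the CRFs and REDCap. That limits what is lost. It does not settle whether the symptom is counted as an AE.

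Two stronger readings are tempting, and the documents support neither. One is that the plan hands an unblinded investigator the choice of what counts. The documents nowhere grant that choice: it would be an inference from the missing tie-break, and the surrounding text points towards recording. The other is that the overlap biases the comparison between arms by some stated amount, or produces false-positive differences at some stated rate. That would need the frequency of mixed changes, the share of mothers with no other AE, and a difference between arms in how the sentences are applied. The documents give none of these. Nor is a direction shown: omitting worsened symptoms everywhere and omitting them unevenly would have different effects.

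**Conclusion.** The overlap is real on the plain wording and is minor. With the slash read as or, 2 of 9 combinations are both exempt and reportable; with the slash read as and, 2 of 9 are covered by neither sentence. No other text resolves it, although the apparent intent was to record such worsening.

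The reach is narrow. It concerns only pre-existing, non-serious maternal symptoms, and chiefly those whose severity and frequency move in opposite directions, within one of several secondary outcomes. New symptoms must be documented in any case, all SAEs go to the sponsor irrespective of relatedness (Section 5.3), and the primary outcome of term delivery with a normal rhythm is untouched. The effect on the AE comparison cannot be calculated from the documents. The conclusion rests on the wording alone and assumes nothing about how sites have in fact applied it.

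**What to change.** Replace the two sentences in Section 5.2 d) with one rule: a pre-existing sign or symptom is documented as an AE if its severity or its frequency is greater than at baseline, whatever the change in the other, and is exempt only if neither is greater. Leave the treatment of new symptoms as it is. In the source list of Section 5.2, replace the slash with or, so that both places say the same thing.

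Under this wording 4 combinations are exempt and 5 are documented, which accounts for all 9 with no overlap and no gap. It restores what the authors apparently meant.

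The cost is two sentences, matching text on the AE worksheet, and slightly more AE worksheets to complete. Baseline severity and frequency are already to be recorded before treatment, and AEs are already reassessed at each encounter, so no extra visit is needed.
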